- Off or low dose (≤ 4 mg/day by Decadron) corticosteroid at least two weeks before the first pre-surgical vaccine
- Adequate organ function within 14 days of study registration including: 1)
 Adequate bone marrow reserve: absolute neutrophil (segmented and bands)
 count (ANC) ≥1.0 x 10⁹/L, absolute lymphocytes ≥400/µL, platelets ≥100 x
 10⁹/L; hemoglobin ≥ 8 g/dL; 2) Hepatic: Total bilirubin ≤ 1.5 x upper limit of
 normal (ULN) and SGPT (ALT) ≤ 2.5 x upper limit of normal (ULN), and 3)
 Renal: Normal serum creatinine or creatinine clearance ≥60 ml/min/1.73 m²
- Must be free of systemic infection. Subjects with active infections (whether or not they require antibiotic therapy) may be eligible after complete resolution of the infection. Subjects on antibiotic therapy must be off antibiotics for at least 7 days before beginning treatment.
- Sexually active females of child bearing potential must agree to use adequate contraception (diaphragm, birth control pills, injections, intrauterine device [IUD], surgical sterilization, subcutaneous implants, or abstinence, etc.) for the duration of the vaccination period. Sexually active males must agree to use barrier contraceptive for the duration of the vaccination period.
- Patient must sign an informed consent document indicating that they are aware
 of the investigational nature of this study, which includes an authorization for
 the release of their protected health information

Key Exclusion Criteria:

- Presence of gliomatosis cerebri, cranial or spinal leptomeningeal metastatic disease
- Presence of T1 Gadolinium (Gd) –enhancing lesions (on MRI) suggestive of high-grade glioma
- Pathological diagnosis for the resected tumor demonstrates transformation to higher grade (i.e. WHO grade III or IV) or gliomas. If a patient who received pre-surgical vaccines is diagnosed as high-grade glioma (HGG), the patient will be withdrawn from the study and considered for therapeutic options for HGG (trials for HGG or standard of care). The tumor tissue of such a case would be brought to the lab before the pathological diagnosis is made; and thus would be processed before the lab is informed of the final HGG diagnosis. Because HGG tissue may still reflect the vaccine effects, we will evaluate the tumor tissue to help us develop future approaches for HGG.
- Pregnant women are excluded from this study. Pregnancy testing will be performed on all menstruating females within 14 days prior to study enrollment

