3.1 Inclusion Criteria

- **3.1.1** Patients must be ≥ 18 years old
- 3.1.2 Pathological criteria Patients must have a newly diagnosed or recurrent WHO grade II astrocytoma, oligoastrocytoma or oligodendriglioma that has been histologically confirmed by prior biopsy or surgical resection. If the pathological diagnosis was made outside of UCSF, the pathology must be reviewed and confirmed at UCSF.
- **3.1.3** Patients must be positive for HLA-A2 based on flow-cytometry or genotyping.
- **3.1.4** Before enrollment, patients must show non-enhancing T2-FLAIR lesions that are amenable to surgical resection. Surgical resection of at least 0.3 grams of tumor is expected to ensure adequate evaluation of the study endpoints.
- 3.1.5 Prior radiation therapy (RT) after initial diagnosis will be allowed but there must be at least 6 months from the completion of RT (or radiosurgery). Prior chemotherapy and any systemic molecularly targeted anti-tumor therapy will be allowed, and there must be at least 28 days from the last temodar chemotherapy, 42 days for nitrosourea; at least 14 days from the last dose for chemotherapy regimens given continuously or on a weekly basis with limited potential for delayed toxicity.

12 April 2020 Page 24 of 88 confidential

- **3.1.6** Karnofsky performance status (KPS) ≥ 70% (Appendix I)
- **3.1.7** Off or low dose (≤ 4 mg/day by Decadron) corticosteroid for at least for 2 weeks before the first pre-surgical vaccine
- 3.1.8 Adequate organ function within 28 days of study registration including:
 Adequate bone marrow reserve: absolute neutrophil (segmented and bands) count (ANC) ≥1.0 x 10⁹/L, absolute lymphocyte count (ANC) ≥4.0 x 10⁸/L, platelets ≥100 x 10⁹/L; hemoglobin ≥ 8 g/dL
 - Hepatic: Total bilirubin \leq 1.5 x upper limit of normal (ULN) for age and SGPT (ALT) \leq 2.5 x upper limit of normal (ULN) for age
 - Renal: Normal serum creatinine or creatinine clearance ≥60 ml/min/1.73 m²
- **3.1.9** Must be free of systemic infection. Subjects with active infections (whether or not they require antibiotic therapy) may be eligible after complete resolution of the infection. Subjects on antibiotic therapy must be off antibiotics for at least 7 days before beginning treatment.

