5.7 Drug Administration Delay, Dose Reduction, and/or Discontinuation (Individual Patients)

5.7.1 Delay in treatment administration

Treatment will be delayed by 1 week if on the day of the planned vaccination

- Patient has a fever of > 101°F (38.3 °C)
- Treatment related side effects have not resolved to grade 1 or better (except for grade 2 lymphopenia and injection site reactions from prior IMA950+poly-ICLC vaccine).

If the continued inflammatory reactions at the injection site remain too severe in both legs to allow subsequent vaccines, the treatment will be suspended for up to 6 weeks from the originally scheduled date for the next vaccine. When the therapy is resumed after a delayed dose, subsequent schedules will be slid back to keep the original intervals. If the situation does not resolve in 6 weeks, this is considered RLT and the patient will be withdrawn from the protocol.

Vaccination will be held for any \geq Grade 2 non-RLT AE (except grade 2 lymphopenia or flu-like symptoms), felt to be related to therapy, until they return to \leq Grade 1.

Possible adverse events by IMA950-poly-ICLC vaccines and varillumab are summarized in Section 5.8. In circumstances where assessment of an adverse event is limited, such as by intercurrent illness, or when laboratory studies are required to assess for other causes of toxicity, the treatment schedule may be interrupted for up to 6 weeks. Delay of one vaccine (and varillumab if scheduled) administration by up to 6 weeks will not be considered a protocol violation if due to an adverse event, regardless of attribution. If one or more treatment cycle is delayed by longer than 6 weeks due to an adverse event, regardless of attribution, treatment must be discontinued.

In the case of hepatic enzyme elevation >4x baseline (which is Grade 2; 3-5 x ULN), or any other unforeseen intolerable side effects of grade 2 (except for flu-like symptoms) or greater but not meeting the RLT criteria in Section 5.3.1, IMA950-poly-ICLC vaccine will be discontinued until that toxicity has reduced to Grade 1 or less. If the vaccine cannot be reinitiated in 6 weeks, the participant will be withdrawn for the RLT.

In the pre-surgical phase:

 If the scheduled craniotomy is delayed longer than 2 weeks secondary to RLT, the patient will be withdrawn from the protocol

12 April 2020 Page 39 of 88 confidential

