Patients with LFT elevations > 8x the upper limit of normal (ULN) that are judged to be due to the study regimen, should initiate high-dose corticosteroid therapy (e.g., methylprednisolone 2 mg/kg once or twice daily or equivalent) and permanently stop administration of all regimen treatment. In patients with > 8x ULN, LFTs should be performed daily until stable or declining for 5 consecutive days. LFTs should be monitored for at least 2 consecutive weeks to ensure sustained treatment response. If symptoms or LFT elevations are controlled, the corticosteroid dose should be gradually tapered over a period of at least 1 month. Flare in LFTs during this taper may be treated with an increase in the dose of steroid and a slower taper.

In patients without response to corticosteroid therapy within 3 to 5 days or who have an LFT flare during steroid tapering that is not responsive to an increase in steroids, addition of immunosuppression with mycophenolate mofetil should be considered after a gastroenterology/hepatology consult. Patients receiving immunosuppression for more than 4 weeks should be evaluated for prophylaxis of opportunistic infections.

Skin: A dermatologist should evaluate persistent or severe rash or pruritus. A biopsy should be performed if appropriate and if possible, photos of the rash should also be obtained. Low grade study therapy-mediated rash and pruritus may be treated with

12 April 2020 Page 52 of 88 confidential

symptomatic therapy e.g., antihistamines). Topical or parenteral corticosteroids may be required for more severe symptoms.

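### The liver-enzyme hold in section 5.7.1 contradicts its own grade range across the permitted entry range, and lies above the permanent-stop level of section 5.8.5 when baseline exceeds 2 × ULN

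*Combined protocol and SAP*

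**What the plan says.** Five rules in the protocol bear on a raised liver enzyme.

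- **Liver clause, section 5.7.1.** The trigger is "hepatic enzyme elevation >4x baseline (which is Grade 2; 3-5 x ULN"). The action is that "IMA950-poly-ICLC vaccine will be discontinued until that toxicity has reduced to Grade 1 or less". No attribution to treatment is required. If the vaccine cannot be restarted in 6 weeks, the participant is withdrawn for RLT.
- **General holds, section 5.7.1.** Vaccination is held for any Grade 2 or higher event of this kind: "Grade 2 non-RLT AE (except grade 2 lymphopenia or flu-like symptoms), felt to be related to therapy". Treatment is also put off by a week if "Treatment related side effects have not resolved to grade 1 or better".
- **RLT definition, section 5.6.1.** With listed exceptions that do not concern liver enzymes, any Grade 3 or higher toxicity at least possibly related to treatment is an RLT, and the patient is taken off study.
- **Work-up, section 5.8.5.** Closer monitoring and investigation start at Grade 2 for a normal baseline, or at twice baseline for a baseline already at Grade 1 or 2. This is not itself a hold.
- **Permanent stop, section 5.8.5.** "Patients with LFT elevations > 8x the upper limit of normal (ULN) that are judged to be due to the study regimen" are to start corticosteroids and "permanently stop administration of all regimen treatment".

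Section 3.1.8 admits ALT up to "2.5 x upper limit of normal (ULN) for age". It sets no AST limit. Section 5.7.1 does not define baseline.

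**The concern.** The parenthesis in the liver clause asserts that two scales are the same. One moves with the patient's baseline and the other does not, so they can agree only over a limited span of baselines. The entry criterion permits baselines well outside that span.

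Two investigators applying the clause to the same laboratory value could then decide differently, one by the multiple and the other by the grade label. Read by the multiple, a temporary hold can also sit above the level for a permanent stop, which reverses the expected order. At the low end, a hold can begin at a value that already satisfies the condition for ending it.

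**Working it through.** **Inputs.** Liver trigger: more than 4 × baseline, labelled Grade 2 and 3-5 × ULN (5.7.1). Highest entry ALT: 2.5 × ULN (3.1.8). Permanent stop: above 8 × ULN if judged due to the regimen (5.8.5). Work-up: 2 × baseline for an abnormal baseline (5.8.5). The lower baselines below are illustrative; the documents give no distribution of entry values.

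**Step 1: the plan's own equivalence.** Let b be baseline in units of ULN. The trigger point is T = 4b. If baseline is taken as exactly 1 × ULN, T = 4 × ULN. That lies inside 3-5 but is still a different rule: a value between 3 and 4 × ULN carries the Grade 2 label and does not trigger. The equivalence is not reproduced.

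**Step 2: where T lies inside the stated range.** 3 ≤ 4b ≤ 5 gives 3/4 ≤ b ≤ 5/4, that is 0.75 to 1.25 × ULN.

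**Step 3: where T lies above the permanent stop.** 4b > 8 gives b > 2.0 × ULN.

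| Baseline (× ULN) | Trigger 4b (× ULN) | Within 3-5? | Above 8? |
|---|---|---|---|
| 0.5 | 2 | no, below | no |
| 0.75 | 3 | yes | no |
| 1.0 | 4 | yes | no |
| 1.25 | 5 | yes | no |
| 1.5 | 6 | no, above | no |
| 2.0 | 8 | no, above | no (equal) |
| 2.5 | 10 | no, above | yes |

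At b = 2.5 the trigger is twice the top of the stated range (10/5 = 2). The permanent-stop level is only 8/2.5 = 3.2 times that baseline.

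**Step 4: the low end.** At b = 0.5 the clause fires above 2 × ULN. On the clause's own scale Grade 2 starts at 3 × ULN. A patient between 2 and 3 × ULN is therefore held while below Grade 2, so the release condition of Grade 1 or less appears already met.

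**Step 5: all the rules at b = 2.5**, graded on the scale in the parenthesis.

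| Rule | Attribution needed? | Level (× ULN) |
|---|---|---|
| General Grade 2 hold and one-week delay, 5.7.1 | yes | from 3 |
| Related Grade 3 RLT, 5.6.1 | yes | above 5 |
| Work-up, 5.8.5 (no hold), if this baseline counts as Grade 1 or 2 | no | 5 (= 2 × 2.5) |
| Permanent stop, 5.8.5 | yes | above 8 |
| Liver clause, 5.7.1 | none stated | above 10 by the multiple; 3-5 by the label |

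For a rise felt to be related, the general hold and the RLT rule come first. For a rise not attributed to treatment, those two rules and the permanent stop do not apply. The liver clause may then be the only automatic hold, and its two readings are far apart: 3 × ULN by the label, 10 × ULN by the multiple.

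**The case against.** The strongest reply is that the rules work together. A reader might infer that a patient who enters at 2.5 × ULN goes unheld until enzymes pass 10 × ULN. The documents do not support that. For a related rise, the general hold acts from 3 × ULN on the parenthesis's own scale, and a rise above 5 × ULN is already an RLT. The reversed order against the permanent stop is likewise a property of the clause taken alone. That stop covers only rises judged due to the regimen, and those are the rises the earlier rules catch. This part of the reply stands.

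The reply can add that the clause carries a Grade 2 label and goes on to other side effects short of RLT, so a sensible reader would treat it as a Grade 2 hold. That is a plausible reading, but it sets aside the multiple of baseline, which is the trigger actually written. Nothing in section 5.7.1 says which part governs, or whether the liver clause or the general hold prevails.

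A reader might also infer that the choice of trigger alters the co-primary RLT count, since a hold lasting beyond 6 weeks ends in withdrawal for RLT. The documents do not show this. Related rises above 5 × ULN are RLTs under either trigger, related rises of 3-5 × ULN are held in any case, and no frequency of raised entry ALT is given.

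Finally, the CTCAE grading table is not reproduced, so how an abnormal baseline is graded cannot be settled from the documents. That limits what can be said about the other rules. It does not rescue the equation in the parenthesis.

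**Conclusion.** The liver clause is wrong as written. Its two expressions agree, as to where the trigger point falls, only for baselines of 0.75-1.25 × ULN, while entry ALT may reach 2.5 × ULN. Read by the multiple, it fires only above 10 × ULN at the entry limit, lies above the permanent-stop level for any baseline above 2 × ULN, and starts below its own Grade 2 range for baselines under 0.75 × ULN.

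The practical conflict is narrower than these figures suggest. It concerns mainly rises not attributed to treatment, patients with low baselines, and the unstated order of precedence between overlapping rules.

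The conclusion assumes that baseline means the patient's own pre-treatment value, and it uses the 3-5 × ULN in the parenthesis as the Grade 2 scale. The example at 2.5 × ULN is the extreme permitted value and applies to ALT, the only transaminase with an entry limit. No effect on the safety endpoint or the stopping rule is claimed.

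**What to change.** The sponsor's clinicians should reconcile the following on one scale, so that grade label, hold, work-up, RLT and permanent stop fall in a consistent order for every eligible baseline:

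- the entry limit in section 3.1.8;
- the RLT definition in section 5.6.1;
- the liver clause and the general Grade 2 hold in section 5.7.1;
- the work-up trigger and the permanent-stop level in section 5.8.5.

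The amended text should also define baseline, say whether the liver clause applies regardless of attribution, and state which rule prevails where two apply. The clause's reference to RLT criteria in section 5.3.1 should point to section 5.6.1, where they are.

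The levels themselves are a clinical decision, and none is proposed here. The change is to protocol wording only, with no effect on sample size or visit schedule.

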5.7.2 Dose reduction (applicable to poly-ICLC only)

If Grade 2 non-RLT AE recurs, poly-ICLC dose will be cut down to 50% of the original dose (0.7 mg). Pretreatment with acetaminophen 650-1000 mg or with any NSAID may be given. If further dosing is well tolerated, the original dose may be subsequently re-instituted at the discretion of the investigator. All dosage changes will be recorded in the treatment log.

Participants may remain on the 50% reduced dose of poly-ICLC for grade 1 or 2 hematologic toxicity, or grade 1 non-hematologic toxicity (except for grade 1 flu-like signs). If at the 50% dose level, there is not additional or new toxicity for a minimum of 2 weeks, the dose may be escalated back to the starting dose at the discretion of the investigator. Subsequent Grade 2 non-hematologic toxicities, should they occur, will require a dose reduction to 50%, and no further escalations will be allowed. If toxicity reoccurs at the reduced dose, the patient will be taken off treatment.

Because the IMA950 peptide vaccine is sequestered locally, and the immune response occurs primarily locally and in the draining lymph nodes, the dose of IMA950 does not need to be scaled up proportionately to the size (by weight or body surface area) of the recipient, as might be done for a drug whose effect is related to its distribution in body fluid. For the same reasons, dose de-escalation or dose reduction is not as meaningful as it would be with a drug with a narrow therapeutic index.

Modifications to the administered dose of varlilumab are not allowed because the proposed dose is considered the minimum biologically active dose, and there is not a dose-escalation plan in the current study.

5.7.3 Discontinuation of the regimen

Vaccine administration will be discontinued in the following situations:

- o An RLT is observed
- o If there is a delay of scheduled craniotomy greater than 2 weeks
- If there is a delay of vaccine dosing greater than 6 weeks due to treatment related toxicity or regimen-limiting toxicity (RLT)

5.8 Expected Risks and Toxicities of IMA950 Vaccination and Poly-ICLC

5.8.1 IMA950

Potential side effects of IMA950

12 April 2020 Page 40 of 88 confidential

As of the cut-off date for information from the CR0902-11 trial with IMA950 (13-Jun-13), a total of 45 patients had been treated with IMA950 plus GM-CSF. A total of 105 AEs considered at least possibly related to either IMA950 or GM-CSF (by the Investigator) have been observed in 28 patients. Twenty-four patients (53%) experienced a related injection site reaction, all of which where CTCAE Grade 1 or 2. Eleven related AEs, including pruritus and macula-papular rash, were seen in the skin and subcutaneous tissue across eight patients. All were CTCAE Grade 1 or 2. Nine patients have experienced 10 Suspected Unexpected Serious Adverse Reactions (SUSARs) considered at least possibly related to either IMP (IMA950 or GM-CSF) by the Investigator or the Sponsor which included neutropenia (two cases of CTCAE Grade 4), maculo-papular rash (CTCAE Grade 2), erythema multiforme (CTCAE Grade 2), anaphylaxis (CTCAE Grade 3), allergic reaction (CTCAE Grade 2), joint pain (CTCAE Grade 2), basal cell carcinoma of skin in situ (CTCAE Grade 1), fever (CTCAE Grade 1) and fatigue (CTCAE Grade 3).

Six patients have been treated in the IMA950-102 trial at the NCI as of the cut-off date (13-Jun-13). 49 AEs have been reported in the trial that have been considered by the Investigator at least possibly related to IMA950, GM-CSF, imiquimod or cyclophosphamide (CY). Injection site reactions were the most common immunization-related AEs, two SARs have been experienced by two patients (Herpes zoster reactivation, CTCAE Grade 3 and Allergic reaction, CTCAE Grade 2).

Allergic reactions or associated events (e.g. rash, pruritus) have been reported in association with IMA950 and the similar vaccines IMA901 and IMA910. From a total of 51 patients treated with IMA950 in both ongoing trials 2 allergic reactions, one anaphylaxis and several cases of rashes and /or pruritus have been reported with suspected relationship to IMA950 and GM-CSF (except for the case in IMA950-102 as GM-CSF was not given with the vaccination preceding the event).

5.8.2 Poly-ICLC

Adverse Events for DC plus poly-ICLC vaccine (UPCI 05-115)67

In a previous Phase 1/2 study of αDC1 vaccine plus intramuscular (i.m.) injection of poly-ICLC (20 mcg/kg)⁶⁷ in 22 patients, there were no grade 3 or 4 toxicities, no deaths on study, and no DLT at any dose through the 1st booster phase (5 additional vaccines following the scheduled 4 initial vaccines). No incidences of autoimmunity were encountered through the 1st booster phase (total 9 vaccines). Toxicity profiles were comparable across dose levels (data not shown). Grade 1 or 2 injection site reactions were the most common (82%). Grade 1 flu-like symptoms, including fatigue (73%), myalgia (32%), fever (23%), chills/rigors (18%) and headache (32%), were common and usually limited to 24 hours after each vaccine. Grade 2 lymphopenia was recorded in one patient (5%).

Adverse Events for peptides plus poly-ICLC vaccine in WHO grade II LGG patients (UPCI 07-057/08-135)⁷⁷

In our pilot study of peptide-based vaccines in combination with i.m. poly-ICLC (20 mcg/kg) in 23 WHO grade II glioma patients with high-risks for recurrence, principal toxicities included grade I and II injection site reactions (100%) and flu-like symptoms (fatigue, myalgia, fever, headache), which were usually limited to 48 hours after each vaccine and were controlled with acetaminophen or ibuprofen. Grade 1 leukopenia developed in 3 patients who previously received chemotherapy with temozolomide. No instances of autoimmunity were encountered. No RLT has been encountered except for one case who presented with Grade 3 fever and fatigue following the 7th vaccine. The symptoms subsided by the use of over-the-counter non-steroidal anti-inflammatory drug by the next day.

Adverse Event List(s) for poly-ICLC (Overall from all human experience)

12 April 2020 Page 42 of 88 confidential

The severity of adverse effects of poly-ICLC depends on several factors including dose, route of injection, and health status of the patient. Early Phase I studies were done to determine the maximum tolerated dose (MTD) under the assumption that this was also the most effective dose. In these studies with advanced cancer patients, it was found that the MTD was about 12 mg/m² i.v. in patients who were not terminally ill. Patients typically showed fevers of 40°C, myalgia, arthralgia, malaise, and some nausea and vomiting. Fever was the primary dose-limiting factor. At this dose, the mean serum type I IFN level was 2000 IU/mL. While exogenous administration rarely attains this level, serum levels of 100 IU/mL after exogenous IFN administration are associated with the same types and degree of adverse effects as high dose poly-ICLC. In most of the early cancer trials, however, about 6 mg/m² poly-ICLC i.v. was generally used. It was subsequently shown that a low dose of poly-ICLC (<1mg/ m²) was better than a high dose for enhancing immune effects, and that the higher dose actually inhibited a number of cell-associated immune functions. It was also found that i.m. injection brought about much milder side effects than i.v. administration. ⁷⁸ More specific side effects of poly-ICLC are listed below. Please note that these are generally at higher doses than the 1.4 mg proposed for this trial.

Discomfort at IM or SC injection site: The most common adverse effect is mild, transient discomfort at the site of i.m. injection. With subcutaneous (s.c.) injections, there is a transient mild to moderate grade 1 or 2 erythematous skin reaction. ⁷³. However, when combined with peptide vaccine plus Montanide s.c., it can produce a transient skin reaction with induration or sterile abscess. Biopsy of such lesions has demonstrated infiltration by T-cells sensitized to the peptide. It is not clear whether such responses are due to the peptide vaccine, poly-ICLC, Montanide, or the combination, but they have not been reported with just peptide and poly-ICLC.

Flu-like symptoms: Approximately 8 to 12 hours after doses of 10 to 50 mcg/kg i.m., patients may develop a mild flu-like syndrome with fever of less than 38°C, which may last for about 12 hours, but responds readily to acetaminophen or aspirin. Mild myalgia, arthralgia, sometimes nausea, and malaise can be present during this period of time. This flu-like syndrome typically diminishes markedly after the first few poly-ICLC treatments. On very rare occasions in the course of treatment, patients who have been tolerating treatment uneventfully may develop a more pronounced fever with chills and malaise (typical of higher dose i.v. poly-ICLC) in response to an i.m. injection. This will typically resolve over 12 to 24 hours, responds to acetaminophen, and does not recur on subsequent dosing.

Hematologic abnormalities: Several cases of transient leukopenia have been reported. Poly-ICLC was restarted after a drug holiday in most cases, but leukopenia recurred in only one patient, with rapid resolution within two days after discontinuation of drug for the second time. High dose Poly-ICLC has been associated with a coagulopathy in dogs, but not in other species including primates. There has been no change in the expected

12 April 2020 Page 43 of 88 confidential

incidence of deep venous thrombosis, pulmonary embolus, or coagulopathy in multiple sclerosis, AIDS or malignant glioma patients on low dose i.m. poly-ICLC. One paralyzed multiple sclerosis patient treated with 100 mcg/kg i.v. suffered a fatal pulmonary embolus, which was not judged to be due to the drug.

Hepatic enzyme elevation: Mild (grade 1), transient (<7 days) hepatic enzyme elevations were described in a trial of 100 mcg/kg poly-ICLC given i.v. in multiple sclerosis patients. In three patients, this was prolonged for >7 days, but in all patients the enzymes returned to normal after temporary discontinuation of the poly-ICLC. Enzyme elevation was not typically seen with doses of 10 to 50 mcg/kg three times weekly. However, one patient receiving 20 mcg/kg three times per week had to be dropped from study because of a transient enzyme elevation that persisted slightly longer than the 4-week protocol cutoff. In addition, preclinical studies have shown increased hepatic NK cells, as well as suppression of the P450 hepatic enzyme system by poly-ICLC, as well as by IFN, but the clinical implications of this finding are not clear. ⁸⁰, ⁸¹

Seizures: Three glioma patients with epilepsy had seizures during a high febrile episode, but recovered uneventfully.

Transient peritumoral edema: In a pilot brain tumor trial, a few patients showed an increase in their gadolinium enhancing lesions after 3-6 months of i.m. poly-ICLC, followed by an apparent tumor response at 6-12 months and prolonged survival on continued treatment. (Salazar, Levy et al, 1996) Decadron was used as needed in first few months of treatment on that study. In a more recent follow-up open study in patients with advanced recurrent gliomas, several patients have shown increased peritumoral edema after several weeks of poly-ICLC therapy. This has resolved in all cases on continued poly-ICLC, with or without concomitant steroids. (Merchant, Young et al, 2000). Biopsy data in at least two patients treated with poly-ICLC also showed a peritumoral inflammatory response. These findings raise the possibility that poly-ICLC may at times be facilitating a relatively early immunologic response to the tumor, perhaps manifested by transient increased edema or gadolinium enhancement.

Multicenter glioma Clinical trial: In a recent multi-center study of glioblastoma patients, 21 of the 24 subjects (88%) receiving 20 mcg/kg poly-ICLC alone three times weekly reported at least one adverse event. The incidence of adverse events was reported by the worst grade for an event for an individual subject. The majority of adverse events were classified as either grade 1 (71 of 104 or 68%) or grade 2 (28 of 104 or 27%) toxicity. There were only 3 of 104 (3%) and 2 of 104 (2%) events reported as a grade 3 or grade 4 event, respectively. The most frequently reported events (toxicities) were fatigue (15 subjects), local 'pain-other' (10 subjects), and myalgia (9 subjects). Only 57 out of 380 events were definitely or probably ascribed to Poly-ICLC. ⁷¹

In a separate trial in patients with multiply-recurrent anaplastic glioma receiving the same dose i.m., all 24 subjects treated (100%) reported at least one adverse event. The majority

12 April 2020 Page 44 of 88 confidential

of adverse events reported were classified as either grade 1 (41 of 63 or 65%) or grade 2 (14 of 63 or 22%). There were 7 of 63 (11%) grade 3 events and only 1 of 63 (2%) grade 4 event. The most frequently reported adverse events were fatigue (9 subjects), transient increases in SGOT, SGPT and alkaline phosphatase (4 subjects each) and pain, type not specified (4 subjects). Only 19 out of 406 events were definitely or probably ascribed to the poly-ICLC ⁷²

S.c. Poly-ICLC in Normal volunteers: In a trial of a single dose of 1.6 mg s.c. poly-ICLC in normal volunteers, no treatment-related, grade 3, or serious adverse events were reported. Nonetheless, volunteers receiving poly-ICLC developed erythema and induration at the site of injection. Systemic reactogenicity included transient flu-like symptoms, such as malaise, headache, fever, and chills, which were generally mild to moderate in severity). In addition, there were no clinically significant changes in complete blood cell counts and serum chemistries, including liver function tests, 3 and 7 d after poly-ICLC administration. ⁷³

Expected Adverse Events for the IMA950+poly-ICLC vaccine

In the vast majority of previous clinical studies, IMA950 and poly-ICLC have been evaluated in combination regimens with immunomodulatory agents. This is the case in the current study combining IMA950 and poly-ICLC. Hence, it may not be possible or informative to list expected AEs for each of IMA950 and poly-ICLC. Hence, the following tables summarize expected AEs for the vaccine composed of the mixture of IMA950 and poly-ICLC based on the past trials as reported to FDA and through communication as well as Phase 1/2 evaluation of αDC1 vaccine in combination with poly-ICLC in patients with recurrent WHO grade III or IV gliomas (UPCI 05-115)⁶⁷; and Pilot study of peptide-based vaccines in combination with poly-ICLC in WHO grade II gliomas with high risk factors (UPCI 07-057 and 08-135)⁷⁷.

Expected AEs that are listed below as Grade 2 do not require expedited reporting. These Grade 2 AEs are required to be reported in routine study data submissions. Grade 3 with hospitalization or 4 AEs on the list should still require expedited reporting. **Table 1** below includes only CTCAE grade 2 or higher toxicities reported. Any grade 2 or higher AE not on this list or in the accompanying text will be considered an unexpected AE.

Table 1Grade 2:

Dermatology/Skin

CTCAE Category	Description					
Constitutional	Fever (in the absence of					
Symptoms	neutropenia)					
Constitutional	Dimara/Chilla					
Symptoms	Rigors/Chills					
Dermatology/Skin	Injection site reaction					

Rash

Metabolic/laboratory	Hepatic enzyme elevation
Pain	Pain - Muscle pain
Pain	Pain - Joint pain
Pain	Pain - Headache
Hematologic	Transient leucopenia (<1 week)

Grade 3:

CTCAE Category	Description
Hematologic	Leukopenia; Anemia
Constitutional	Fatigue (lethargy, malaise,
Symptoms	asthenia)
Neurology	Peritumoral Edema
Skin	Urticaria

